7.3.3 Secondary Safety Criterion

The secondary safety criterion is diagnosis of SCC and other neoplasia in the treatment field over a 3-year period and will be analysed like the primary safety endpoint.

SCC and other neoplasia are diagnosed by biopsy and include the following diagnoses

- Invasive SCC
- Basal Cell Carcinoma (BCC)
- In Situ BCC/Bowen
- Other neoplasia

The diagnoses “Actinic Keratosis” and “No malignant findings” are not neoplasia events.

The analysis will be presented for the safety analysis set. In addition, the analysis will be presented for the PP analysis set using PP censoring. Please see the analysis set definition document for details.

The CCTP states

“A landmark analysis, conditional on patients’ responses at Week 20, will additionally be performed in order to exclude SCC and other neoplasia reported within the first 20 weeks which are not assumed to be associated with the study treatment. Patients who experience a neoplasia before the 20-week landmark time point are excluded from the time-to-event analysis, which is otherwise conducted as above.”

Diagnosis of SCC and other neoplasia in the treatment field from Week 20 onward will be analysed as described above.

7.3.4 Other Safety Criteria

Physical examination will be summarised by visit.

7.3.5 Adverse Events

Adverse events (AEs) will be presented as described in the CCTP.

Trial ID: LP0041-63	Date: 28-AUG-2019	Version: Final 1.0 Page 12 of 32
---------------------	--------------------------	-------------------------------------

An AE will be considered treatment emergent if the event emerges during treatment having been absent pre-treatment or worsens relative to the pre-treatment state. This is as defined in ICH E9.

Skin malignancies inside the treatment area are defined using Medical Dictionary for Regulatory Activities (MedDRA) v 15.1 as AEs from the Standardised MedDRA Query (SMQ) *skin malignant tumours*. Skin malignancies inside the treatment area will be presented by PT.

7.3.6 Local Skin Responses

Local Skin Responses (LSRs) will be presented as described in the CCTP.

7.3.7 Laboratory Data

Urine pregnancy test data will be listed.

7.4 Analysis of Efficacy

All efficacy analyses will be carried out for the FAS and the PP analysis set unless otherwise stated.

7.4.1 Efficacy Criteria

The efficacy criteria as defined in the CCTP are the following secondary criteria

- Complete AK clearance after the last treatment cycle (at Week 8 or 16)
- Partial (at least 75%) AK clearance after the last treatment cycle (at Week 8 or 16)
- Complete AK clearance at 12 months, defined as no AKs in the selected treatment area at any time from the last treatment cycle at Week 8 or 16 through to Month 12.

The criteria will be analysed as described in the CCTP.

Complete and partial clearance will be summarised by visit with 95% CI of clearance percentage.

Percent reduction in AK count will be summarised by visit.

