#### AK lesion count

Recording of the number of clinically visible AK lesions identified in the selected treatment area on Day 1, Weeks 8, 16 (if retreated), and 20, and Months 12, 18, 24, 30 and 36.

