**Treatment Period (Day 1 to Week 16)**

At Day 1 (Visit 2), the subject eligibility will be confirmed and subjects will be randomised to treatment with either ingenol mebutate gel or imiquimod cream. The selected treatment area will be marked on the skin and the first dose will be applied under the supervision and management of the trial personnel. Subsequent doses will be applied at home.

At the next visits (Day 4 and Weeks 2 and 4; Visits 3 to 5) a clinical assessment of the selected treatment area will be performed. The selected treatment area will be assessed for local skin responses (LSRs) and any adverse events (AEs). If there is suspicion of SCC, BCC, or other neoplasia when clinical assessment is performed, a biopsy will be taken and trial treatment will be stopped but the subject will remain in the trial. At Week 8 (Visit 6), a clinical assessment of the selected treatment area will be performed as for previous visits. An AK count in the selected treatment area will also be conducted.

At Week 8, subjects who are completely cleared in the selected treatment area will continue into the Follow-up Period. Subjects, who are not completely cleared in the selected treatment area will have a second treatment cycle and will attend visits at Week 8+3 days and Weeks 10, 12, and 16 (Visits 7 to 10). The assessments will be the same as during the first treatment cycle. After the second treatment cycle subjects will enter the Follow-up Period.

Until the Follow-up period (Week 20), no other treatments and procedures are allowed in, and within 5 cm of the selected treatment area. Outside the selected treatment area (up to within 5 cm), procedures such as cryotherapy will be allowed; field therapy will not be allowed.

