**Follow-up Period (Week 16 to Month 36).**

Visits will be performed at Week 20 and Months 12, 18, 24, 30 and 36 (Visits 11 to 16), at which a clinical assessment of neoplasia in the selected treatment area will be performed. If there is suspicion of SCC, BCC, or other neoplasia when clinical assessment is performed, a biopsy will be taken. An AK count in the selected treatment area will be conducted.

From Week 20 until Month 36 procedures such as cryotherapy will be allowed in, and within 5 cm of the selected treatment area. Further, at the discretion of the Investigator and according to nationally available product and treatment guidelines, the same treatment as originally administered is allowed (imiquimod or ingenol mebutate). Cross-over between imiquimod

and ingenol mebutate is not allowed. Investigators will be encouraged to pursue these treatment options where clinically relevant before employing other treatments.

Outside the selected treatment area (up to within 5 cm) all treatments will be allowed, although investigators will be encouraged to avoid cross-over between imiquimod and ingenol mebutate.

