### **Concomitant Medication, Treatments and Procedures from Week 20 in the Follow-up Period:**

In the Follow-up Period information will be collected regarding:

- concomitant medications, treatments and procedures used in the selected treatment area
- all use of ingenol mebutate or imiquimod whether inside or outside the selected treatment area
- medication or treatments which may suppress the immune system in the subjects

Procedures such as cryotherapy will be allowed in, and within 5 cm of the selected treatment area. Further, at the discretion of the Investigator and as according to nationally available product and treatment guidelines, the same treatment as originally administered is allowed (imiquimod or ingenol mebutate). Cross-over between imiquimod and ingenol mebutate is **not** allowed. Investigators will be encouraged to pursue these treatment options where clinically relevant and before employing other treatments.

Outside the selected treatment area (up to within 5 cm) all treatments will be allowed, although investigators will be encouraged to avoid cross-over between imiquimod and ingenol mebutate.

No other information on concomitant medications, treatments or procedures will be collected for subjects.

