Table 2-51 Conversion of LSRs to MedDRA by SOC and PT: safety analysis set

LSRs

Table 2-52 – 2-57: Frequency of LSR component <component> by visit: safety analysis set

Table 2-58 – 2-63: Frequency of LSR component <component> by anatomical location and visit: safety analysis set

Table 2-64 Composite LSR score by visit: safety analysis set

Table 2-65 Composite LSR score by anatomical location and visit: safety analysis set

Table 2-66 Change in composite LSR score from baseline by visit: safety analysis set

Table 2-67 Summary of visits of maximum post baseline composite LSR score: safety analysis set

Table 2-68 Maximum post baseline LSR score by LSR component: safety analysis set

Table 2-69 Maximum post baseline composite LSR score: safety analysis set

Other safety endpoints

Table 2-70 Physical examination by visit: safety analysis set

Figures

Figure 2-1 Time to SCC: safety analysis set [[Shell 10](#)]

Figure 2-2 Time to SCC: per protocol analysis set [[Shell 10](#)]

Figure 2-3 Time to SCC or other neoplasia: safety analysis set [[Shell 10](#)]

Figure 2-4 Time to SCC or other neoplasia: per protocol analysis set [[Shell 10](#)]

Figure 2-5 Composite LSR score mean profile by visit: safety analysis set

Figure 2-6 LSR components by visit: safety analysis set

Tables and Figures, Efficacy Data (Module 4)

Tables

Table 3-1 Complete clearance by visit: full analysis set [[Shell 11](#)]

Table 3-2 Complete clearance by visit: per protocol analysis set [[Shell 11](#)]

Table 3-3 Analysis of complete clearance after the last treatment cycle: full analysis set [[Shell 12](#)]

Table 3-4 Analysis of complete clearance after the last treatment cycle: per protocol analysis set [[Shell 12](#)]

Table 3-5 Analysis of complete clearance at Month 12: full analysis set [[Shell 12](#)]

Table 3-6 Analysis of complete clearance at Month 12: per protocol analysis set [[Shell 12](#)]

Table 3-7 Partial clearance by visit: full analysis set [[Shell 11](#)]

Table 3-8 Partial clearance by visit: per protocol analysis set [[Shell 11](#)]

Table 3-9 Analysis of partial clearance after the last treatment cycle: full analysis set [[Shell 12](#)]

Table 3-10 Analysis of partial clearance after the last treatment cycle: per protocol analysis set [[Shell 12](#)]

Table 3-11 Analysis of partial clearance at Month 12: full analysis set [[Shell 12](#)]

Table 3-12 Analysis of partial clearance at Month 12: per protocol analysis set [[Shell 12](#)]

Figures

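### Complete clearance at 12 months has no rule for treatment given in the area between Week 20 and Month 12, so a recurrence that arises and is treated clear in that gap would be scored as sustained clearance

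*SAP*

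**What the plan says.** **Definition.** SAP 7.4.1, in line with Protocol 9.2 and 10.8.1, sets the criterion as "Complete AK clearance at 12 months, defined as no AKs in the selected treatment area at any time from the last treatment cycle" (Week 8 or 16), with the interval ending at Month 12. This is a sustained-clearance endpoint, not a reading at one visit.

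**Counts.** The protocol synopsis (AK lesion count) places AK counts "on Day 1, Weeks 8, 16 (if retreated), and 20, and Months 12, 18, 24, 30 and 36". The follow-up schedule (Protocol 3.1.2 and 10.7.1) has no visit between Week 20 and Month 12.

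**Treatment in the area.** Up to Week 20, Protocol 10.1.2 states that "no other treatments and procedures are allowed in, and within 5 cm of the selected treatment area". After that the position changes: "From Week 20 until Month 36 procedures such as cryotherapy will be allowed in, and within 5 cm of the selected treatment area". The same section also allows repeat use of the product first given. Protocol 10.6.11 says that treatments and procedures used in the selected treatment area will be recorded during follow-up.

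**Analysis.** SAP 7.4.1 refers back to the protocol for the method. Protocol 10.10.4 gives a stratified Cochran–Mantel–Haenszel comparison and a ratio of rates with a 95% confidence interval. SAP 7.5.3 adds no imputation for this endpoint. Shell 12 names one exclusion (subjects not clear at Week 8 who by mistake were not retreated) and labels the analysis only as at month 12. The only efficacy listing in SAP Appendix I is the AK lesion count. None of these places says how treatment in the area after Week 20 enters the 12-month endpoint.

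**The concern.** The definition covers a whole interval, but the planned efficacy data sample it at a few visits. The longest unsampled stretch is also when AK treatment in the area first becomes permissible. Consider a subject who is clear at Week 8 or 16 and at Week 20, recurs later, is treated, and is clear at Month 12. Every scheduled count is zero. An analysis built on the counts passes this subject, although the endpoint as written was failed.

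What is at stake is the 12-month complete clearance rate in each arm and the ratio of the two, for a secondary endpoint that is formally compared. The trial is open-label, and treatment after Week 20 is at the investigator's discretion, so its use may differ between arms. Protocol 5.3 expects many subjects to need further treatment after the randomised period and is itself concerned about confounding.

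**Working it through.** **The plan's own figure.** The documents give no planning figure for clearance. The only one is the precision of the 3-year SCC rate with 240 per arm. It reproduces as a two-sided Wald limit:

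- 1.0% + 1.96 × √(0.01 × 0.99 / 240) = 2.26% (stated 2.26%)
- 2.5% + 1.96 × √(0.025 × 0.975 / 240) = 4.48% (stated 4.48%)

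It does not depend on the present point.

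**Length of the gap.** Month 12 is 365.25 days (12 × 30.4375, the month length in SAP 7.3.2) and Week 20 is day 140.

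- 365.25 − 140 = 225 days, or 32.2 weeks.
- With both visit windows of ±14 days, the range is 197 to 253 days.

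**Which recurrences can be missed.**

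| When the AK is present | Counted? | Treatment allowed in the area? | Result |
|---|---|---|---|
| After the last cycle (Week 8 or 16) | Yes | No | Fails |
| At Week 20 | Yes | Only from then on | Fails, whatever follows |
| Arises after Week 20, treated clear before Month 12 | No | Yes | Zero counts, scored as cleared |
| Present at Month 12 | Yes | Yes | Fails |

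Only the third row is affected.

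**Illustration of size.** Overstatement in an arm = c × r × s × t, where:

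- c is the share clear after the last cycle. Assumed 50%.
- r is recurrence among cleared subjects: 35/128 = 27.3% at one year (imiquimod label, Protocol Appendix V, section 5.1).
- s is the share of recurrences arising after Week 20. Assuming uniform onset, counting from Week 8 gives 32.2/44.2 = 73%, and from Week 16 gives 32.2/36.2 = 89%.
- t is the share of those treated and clear by Month 12. Assumed 20% to 50%.

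Results:

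- Low: 0.50 × 0.273 × 0.73 × 0.20 = 2.0 points, about 5 of 240 subjects.
- High: 0.50 × 0.273 × 0.89 × 0.50 = 6.1 points, about 15 of 240 subjects.
- True sustained rate: 0.50 × (1 − 0.273) = 36.3%, so the reported rate would be about 38.3% to 42.4%.

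With wider assumptions (c from 40% to 60%, t from 10% to 50%):

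- Low: 0.40 × 0.273 × 0.73 × 0.10 = 0.8 points.
- High: 0.60 × 0.273 × 0.89 × 0.50 = 7.3 points.
- That is about 2 to 18 of 240 subjects per arm.

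**Direction of the ratio.** Assume recurrence of 40% against 27%, with half of the recurrences in each arm treated clear in the gap.

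- Equal initial clearance: true ratio 0.60/0.73 = 0.82, observed 0.80/0.865 = 0.92. This moves toward 1.
- Initial clearance ratio of 1.2: true ratio 1.2 × 0.60/0.73 = 0.99, observed 1.2 × 0.80/0.865 = 1.11. This moves away from 1.

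The plan therefore does not fix the direction.

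**The case against.** The strongest reply is that the definition is not tied to scheduled counts. A recurrence documented between visits already fails on the literal wording, and no passage says that treated recurrences are to be counted as clear. That is correct. The defect is the absence of any stated link between the treatment records and the endpoint. The reply does not remove the problem, because the scheduled count is the only AK measure the SAP plans to use, and a programmer following it would pass these subjects.

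The size is also open to challenge, and this stands. The documents give neither clearance rates for this trial nor treatment use after Week 20. The 27% is for imiquimod only. It covers a full year, while the window from Week 8 or 16 to Month 12 is 44 or 36 weeks, so using it unscaled leans high. The treated share has no source: no visit falls in the gap, and AK recurrence is not among the listed grounds for an unscheduled visit (Protocol 10.1.3).

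The per-protocol set is not a clear safeguard. Permitted treatment is not evidently a deviation, the details are in a separate document, and the full analysis set is affected in any case.

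A reader might infer three stronger points that the documents do not support:

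- **Every recurrence treated before Month 12 is counted as clearance.** AKs counted at Week 16 or Week 20 already fail.
- **The ratio is pulled toward 1.** The second example above moves away from 1.
- **Partial clearance at Month 12 has the same defect.** It appears only in the table list ("Analysis of partial clearance at Month 12: full analysis set" and its per-protocol counterpart) and carries no condition over the interval. Counting AKs regardless of permitted treatment is a legitimate choice there.

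**Conclusion.** The point holds for complete clearance at 12 months, and for recurrences that both arise and are treated clear between the Week 20 and Month 12 counts. For those subjects a count-based analysis contradicts the plan's own definition, so this is more than a free choice of estimand.

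The overstatement is about 2 to 6 percentage points per arm under the assumptions listed, none of which the trial documents confirm. If little treatment is given in the gap, the effect is close to zero. The effect on the between-arm ratio cannot be signed in advance. This is a secondary efficacy endpoint, and the primary SCC analysis and the sample size are untouched. The change is worth making because it is cheap and, without it, a reader of the report could not tell which rule was applied.

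**What to change.** Add to SAP 7.4.1, for complete clearance at 12 months only: any recorded cryotherapy, ingenol mebutate, imiquimod or other AK therapy from a stated list, used in the selected treatment area from Week 20 up to the Month 12 count, counts as not cleared. Present the count-only result as a sensitivity analysis. Repeat the condition covering the whole interval in Tables 3-5 and 3-6 and in Shell 12.

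The treatments should be named in a list. Protocol 10.6.11 asks for the reason for treatment up to Week 20 but does not mention it for follow-up, so a rule based on intent may not be programmable.

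The cost is one SAP sentence, some relabelling and one extra table per analysis set, using data already collected. The reported clearance rate will be slightly lower, and a few procedures not aimed at AKs may be misclassified as failures. The sensitivity analysis will show how much that matters.

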7.5 General Principles

7.5.1 Statistical Analysis

In general, all output will be presented by treatment group where nothing else is mentioned. Descriptive statistics for all endpoints will be presented by treatment group and visit (if applicable) using observed cases, i.e. no imputation of missing data will be performed. Summaries by subgroup will include presentation of the endpoint in question by subgroup and overall.

Continuous data will be presented using the number of subjects, mean, standard deviation (SD), median, minimum, and maximum as described in the protocol. In addition, lower and upper quartile will be presented. Both the absolute values and the relative change from baseline will be presented.

Statistical tests will be performed as described in the protocol unless otherwise detailed.

Medical history and AEs are coded using MedDRA version 15.1.

7.5.2 Pooling of Trial Sites

There will be no pooling of trial sites.

7.5.3 Handling of Drop-outs and Missing Values

Drop-outs will be handled as described in section 7.3.1 for the primary and secondary safety criteria using censoring in time-to-event analyses.

Missing results from biopsies will be handled using censoring as described in section 7.3.1.

Besides this, no imputation will be implemented.

7.5.4 Incomplete Dates

The following rules apply for incomplete dates.

Adverse events

- AE start day is missing but not AE start month and year:
 - If the year and month of AE start is before the year and month of exposure start, or if AE end date is complete and before exposure start, then the AE will not be considered treatment emergent.

- If the year and month of AE start is the same as the year and month of exposure start, then the AE will be considered treatment emergent, unless the AE has a complete end date which is before exposure start.
- If the year and month of the AE start is after the year and month of exposure start, then the AE will be considered treatment emergent.
- AE start month is missing but not AE start year:
 - If the year of AE start is before the year of exposure start, or AE end month and year are not missing and are before the month and year of exposure start, or if AE has a complete end date which is before the exposure start date, then the AE will not be considered treatment emergent.
 - If the year of AE start is the same as the year of exposure start, then the AE will be considered treatment emergent, unless the AE end month and year are not missing and are before the month and year of exposure start or AE has a complete end date which is before the exposure start date.
 - If the year of AE start is after the year of exposure start, then the AE will be considered treatment emergent.

Concomitant medication

- Incomplete CM start dates:
 - If the start day is missing but not the start month and year, it will be assumed that the start day is the first day of the month.
 - If the start day and month are missing but not the start year, it will be assumed that the start day is 01 January.
 - If the start day, month, and year are missing, it will be assumed that the medication was started before trial start.
- Incomplete CM end dates:
 - If the end day is missing but not the end month and year, it will be assumed that the end day is the last day of the month.
 - If the end day and month is missing but not the end year, it will be assumed that the end day was 31 December.
 - If the end day, month, and year is missing, it will be assumed that the medication was ongoing at the end of the trial.

7.5.5 Treatment Labels

The following labels will be used for the two treatment groups:

Table 3: Treatment labels for the clinical trial report text and tables

Label Used in Text	Label Used in Tables	Order in Table
Ingenol mebutate	Ingenol mebutate	1
Imiquimod	Imiquimod	2

7.5.6 Changes to the Protocol

- The CCTP states: “*An interim analysis of trial data, obtained when approximately half of the trial period has elapsed, will be conducted. Assuming the time schedule shown in section 10.2, this will be prepared 3 years after study start. The interim analysis will not impact the conduct of this trial.*” This interim analysis was not conducted since the Pharmacovigilance Risk Assessment Committee at the European Medicines Agency found that the Periodic Safety Update Report was satisfactory.
- The CCTP states: “*A per protocol (PP) analysis set will be used as safety and efficacy subsets and will be defined as subjects in the FAS who complete the trial without major protocol deviations.*” Only deviations having impact on safety or efficacy will be considered. As the primary analysis is a time-to-event analysis, subjects will be censored from the PP analysis at the time of the deviation, i.e. the subject will be in the PP analysis set until the day when the deviation takes place.
- To support the primary endpoint, descriptive statistics of demographic and other baseline characteristics will be presented for the safety analysis set and not for the FAS as described in the CCTP.
- Reason for premature discontinuation from treatment is not presented as it is not captured in the eCRF. Reason for not applying trial medication according to protocol is listed.

Appendix I
Tables, Figures and Listings

Tables and Figures, Baseline Characteristics and Investigational Product Data (Module 2)

Tables

Table 1-1	Subject enrollment and randomisation by country and trial site: enrolled subjects
Table 1-2	Subject disposition: safety analysis set [Shell 1]
Table 1-3	Reasons for withdrawal from trial: safety analysis set
Table 1-4	Reasons for withdrawal from trial by last visit attended: safety analysis set
Table 1-5	Protocol deviations leading to exclusion from per protocol analysis set: full analysis set
Table 1-6	Age, height, weight, and BMI: safety analysis set
Table 1-7	Sex, race, ethnicity, and skin type: safety analysis set
Table 1-8	Anatomical location of treatment area: safety analysis set
Table 1-9	AK count at baseline by anatomical location: safety analysis set
Table 1-10	Duration of AK: safety analysis set
Table 1-11	Medical history by SOC and PT: safety analysis set
Table 1-12	AK treatment history: safety analysis set
Table 1-13	History of SCC: safety analysis set [Shell 2]
Table 1-14	Concurrent diagnoses: safety analysis set
Table 1-15	Concomitant medication at baseline: safety analysis set
Table 1-16	Concomitant treatment and procedures at baseline: safety analysis set
Table 1-17	Vital signs at baseline: safety analysis set
Table 1-18	Treatment compliance with protocol: safety analysis set
Table 1-19	Exposure – number of treatment cycles by country: safety analysis set [Shell 3]
Table 1-20	Exposure – number of treatment cycles by anatomical location: safety analysis set [Shell 3]
Table 1-21	Exposure – number of treatment cycles by history of SCC: safety analysis set [Shell 3]

Tables and Figures, Safety Data (Module 3)

Tables

Histology

- Table 2-1 Histological diagnoses of biopsies: safety analysis set [[Shell 4](#)]
- Table 2-2 Histological diagnoses of biopsies: per protocol analysis set [[Shell 4](#)]
- Table 2-3 Incidence of SCC in the treatment area from baseline to month 36: safety analysis set [[Shell 5](#)]
- Table 2-4 Incidence of SCC in the treatment area from baseline to month 36: per protocol analysis set [[Shell 5](#)]
- Table 2-5 Incidence of SCC and other neoplasia in the treatment area from baseline to month 36: safety analysis set [[Shell 5](#)]
- Table 2-6 Incidence of SCC and other neoplasia in the treatment area from baseline to month 36: per protocol analysis set [[Shell 5](#)]
- Table 2-7 Annual incidence of SCC in the treatment area: safety analysis set [[Shell 6](#)]
- Table 2-8 Annual incidence of SCC in the treatment area: per protocol analysis set [[Shell 6](#)]
- Table 2-9 Summary of SCC in the treatment area from baseline to end of trial: safety analysis set [[Shell 7](#)]
- Table 2-10 Summary of SCC in the treatment area from baseline to end of trial: per protocol analysis set [[Shell 7](#)]
- Table 2-11 Annual incidence of SCC and other neoplasia in the treatment area: safety analysis set [[Shell 6](#)]
- Table 2-12 Annual incidence of SCC and other neoplasia in the treatment area: per protocol analysis set [[Shell 6](#)]
- Table 2-13 Incidence of SCC in the treatment area by subgroups: safety analysis set [[Shell 8](#)]
- Table 2-14 Incidence of SCC in the treatment area by subgroups: per protocol analysis set [[Shell 8](#)]
- Table 2-15 Incidence of SCC and other neoplasia in the treatment area by subgroups: safety analysis set [[Shell 8](#)]
- Table 2-16 Incidence of SCC and other neoplasia in the treatment area by subgroups: per protocol analysis set [[Shell 8](#)]
- Table 2-17 Incidence of SCC and other neoplasia in the treatment area from week 20 to month 36: safety analysis set [[Shell 5](#)]

Trial ID: LP0041-63	Date: 28-AUG-2019	Version: Final 1.0 Page 19 of 32
---------------------	--------------------------	-------------------------------------

Table 2-18 Incidence of SCC and other neoplasia in the treatment area from week 20 to month 36: per protocol analysis set [[Shell 5](#)]

Table 2-19 Difference in the incidence of SCC in the treatment area: safety analysis set [[Shell 9](#)]

Table 2-20 Difference in the incidence of SCC in the treatment area: per protocol analysis set [[Shell 9](#)]

Table 2-21 Difference in the incidence of SCC and other neoplasia in the treatment area: safety analysis set [[Shell 9](#)]

Table 2-22 Difference in the incidence of SCC and other neoplasia in the treatment area: per protocol analysis set [[Shell 9](#)]

Adverse events

Table 2-23 Overall summary of adverse events from start of treatment to end of trial: safety analysis set

Table 2-24 Overall summary of adverse events from start of treatment to Week 20: safety analysis set

Table 2-25 Overall summary of adverse events from Week 20 to end of trial: safety analysis set

Table 2-26 Overall summary of adverse events by period: safety analysis set

Table 2-27 Adverse events from start of treatment to Week 20 by SOC: safety analysis set

Table 2-28 Adverse events by SOC: safety analysis set

Table 2-29 Adverse events from start of treatment to Week 20 by SOC and PT: safety analysis set

Table 2-30 Adverse events from Week 20 to end of trial by SOC and PT: safety analysis set

Table 2-31 Frequent adverse events ($\geq 5\%$ in any treatment group) from start of treatment to Week 20 by SOC and PT: safety analysis set

Table 2-32 Frequent adverse events ($\geq 5\%$ in any treatment group) from Week 20 to end of trial by SOC and PT: safety analysis set

Table 2-33 Adverse events from start of treatment to Week 20 by severity, SOC, and PT: safety analysis set

Table 2-34 Adverse events from Week 20 to end of trial by severity, SOC, and PT: safety analysis set

Table 2-35 Related adverse events from start of treatment to Week 20 by SOC and PT: safety analysis set

Table 2-36 Related adverse events from Week 20 to end of trial by SOC and PT: safety analysis set

Trial ID: LP0041-63	Date: 28-AUG-2019	Version: Final 1.0 Page 20 of 32
---------------------	--------------------------	-------------------------------------

Table 2-37 Related adverse events from start of treatment to Week 20 by severity, SOC, and PT: safety analysis set

Table 2-38 Related adverse events from Week 20 to end of trial by severity, SOC, and PT: safety analysis set

Table 2-39 Related adverse events by period, SOC, and PT: safety analysis set

Table 2-40 Adverse events from start of treatment to Week 20 by causal relationship, SOC, and PT: safety analysis set

Table 2-41 Adverse events from Week 20 to end of trial by causal relationship, SOC, and PT: safety analysis set

Table 2-42 Serious adverse events from start of treatment to Week 20 by SOC and PT: safety analysis set

Table 2-43 Serious adverse events by SOC and PT: safety analysis set

Table 2-44 Serious adverse events from start of treatment to Week 20 by causal relationship, SOC, and PT: safety analysis set

Table 2-45 Serious adverse events from Week 20 to end of trial by causal relationship, SOC, and PT: safety analysis set

Table 2-46 Skin malignancies inside treatment area by PT: safety analysis set

Table 2-47 Skin malignancies outside treatment area by PT: safety analysis set

Table 2-48 Adverse events leading to withdrawal from trial by SOC and PT: safety analysis set

Table 2-49 Adverse events from start of treatment to Week 20 by outcome: safety analysis set

Table 2-50 Adverse events from Week 20 to end of trial by outcome: safety analysis set

Table 2-51 Conversion of LSRs to MedDRA by SOC and PT: safety analysis set

LSRs

Table 2-52 – 2-57: Frequency of LSR component <component> by visit: safety analysis set

Table 2-58 – 2-63: Frequency of LSR component <component> by anatomical location and visit: safety analysis set

Table 2-64 Composite LSR score by visit: safety analysis set

Table 2-65 Composite LSR score by anatomical location and visit: safety analysis set

Table 2-66 Change in composite LSR score from baseline by visit: safety analysis set

Table 2-67 Summary of visits of maximum post baseline composite LSR score: safety analysis set

Table 2-68 Maximum post baseline LSR score by LSR component: safety analysis set

Table 2-69 Maximum post baseline composite LSR score: safety analysis set

Other safety endpoints

Table 2-70 Physical examination by visit: safety analysis set

Figures

Figure 2-1 Time to SCC: safety analysis set [[Shell 10](#)]

Figure 2-2 Time to SCC: per protocol analysis set [[Shell 10](#)]

Figure 2-3 Time to SCC or other neoplasia: safety analysis set [[Shell 10](#)]

Figure 2-4 Time to SCC or other neoplasia: per protocol analysis set [[Shell 10](#)]

Figure 2-5 Composite LSR score mean profile by visit: safety analysis set

Figure 2-6 LSR components by visit: safety analysis set

Tables and Figures, Efficacy Data (Module 4)

Tables

Table 3-1 Complete clearance by visit: full analysis set [[Shell 11](#)]

Table 3-2 Complete clearance by visit: per protocol analysis set [[Shell 11](#)]

Table 3-3 Analysis of complete clearance after the last treatment cycle: full analysis set [[Shell 12](#)]

Table 3-4 Analysis of complete clearance after the last treatment cycle: per protocol analysis set [[Shell 12](#)]

Table 3-5 Analysis of complete clearance at Month 12: full analysis set [[Shell 12](#)]

Table 3-6 Analysis of complete clearance at Month 12: per protocol analysis set [[Shell 12](#)]

Table 3-7 Partial clearance by visit: full analysis set [[Shell 11](#)]

Table 3-8 Partial clearance by visit: per protocol analysis set [[Shell 11](#)]

Table 3-9 Analysis of partial clearance after the last treatment cycle: full analysis set [[Shell 12](#)]

Table 3-10 Analysis of partial clearance after the last treatment cycle: per protocol analysis set [[Shell 12](#)]

Table 3-11 Analysis of partial clearance at Month 12: full analysis set [[Shell 12](#)]

Table 3-12 Analysis of partial clearance at Month 12: per protocol analysis set [[Shell 12](#)]

Figures

Figure 3-1 Complete clearance by visit: full analysis set

Figure 3-2 Partial clearance by visit: full analysis set

Figure 3-3 AK count by visit: full analysis set

Trial ID: LP0041-63	Date: 28-AUG-2019	Version: Final 1.0 Page 22 of 32
---------------------	--------------------------	-------------------------------------

Patient Data Listings (Appendix 1)

